9.5.4 Exploratory Endpoints

9.5.4.1 Proctor Support

Descriptive statistics will be presented for participants who requested proctor support on the Day 57 Visit and for participants who completed the Day 57 Visit without using the proctor support in the PPS, for the following primary and secondary endpoints:

- Sample integrity
- Reliability
- Safety
- Usability

Statistical Analysis Plan (SAP)

Protocol: Phase 1 Study Evaluating Technologies for Point-of-Care Blood Collections in Support of Decentralized Outpatient Assessments in Pandemic and Clinical Trial Settings

Version Date: 27-Jun-2025

Sponsor: Resilience Government Services, Inc.

Protocol No: 5309/0024

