Decentralized (eg, home) ^b		X	X	X
Proctor session ^c		X ^c	(X) ^c	
Training	X ^c	X ^c	(X) ^c	
Informed consent (eConsent)	X			
Demographics	X			
Medical history ^d	X			
Concomitant medication	X	X	X	X
Vital signs ^e	X			
Physical examination ^f	X			
Pregnancy urine test (females only)	X			
Eligibility check	X			
Randomization (IVRS)	X			
COVID-19 symptom screen ^g	X		X	X
Nasopharyngeal swab for SARS-CoV-2 PCR ^h	X			
Tasso+™ collection				
SST capillary collection tube (left upper arm preferred)	X ^{il}	X ^{jl}	X ^{kl}	X ^{kl}
EDTA capillary collection tube (right upper arm preferred)	X ^{il}	X ^{jl}	X ^{kl}	X ^{kl}
Venous blood collection				
SST tube	X ^{im}			
EDTA tube	X ^{im}			

Sponsor Name: Resilience Government Services, Inc., [name]

Protocol Number: 5309/0024

Protocol Version and Date: Version 3.0 – 17 Jan 2025

Assessments		Visits ^a			
Study Day (±visit window)		Visit 1	Visit 2	Visit 3	Visit 4
		1	29±3	57±3	85±3
eDiary					
Tasso questionnaire (user experience)	X		X	X	X
Symptom questionnaire (AEs/SAEs) ⁿ	X		X	X	X

AE=adverse event; EDTA=ethylenediaminetetraacetic acid; IFU=instruction for use; IVRS=interactive voice response system; HCP=healthcare professional; PCR=polymerase chain reaction;

SAE=serious adverse event; SST=serum-separator tube

Footnotes:

a If a participant withdraws from the study early, the assessments planned for the last follow-up/end of study Visit should be completed at the time of withdrawal.

b Defined as any remote location of convenience for the participant where the administration can be done with appropriate technique in a clean environment where samples can be packaged for shipment.

c When administering the Tasso+™ remotely, participants will receive proctor-support on Day 29 (and as requested, on Day 57), the intent being to guide the participant through the process and to help troubleshoot should any difficulties be encountered. Proctor sessions will be prescheduled by the Site to take place during working hours. Training will be performed on Day 1 (by Site) and Day 29 (by Proctor). Training on Day 57 should be performed only if requested by the participant. Training may include detailed IFU and online video training (see [Section 7.4](#) and IFU provided separately). While assistance will be available to the participant during Day 57 Visit, it is of interest to know whether the prior trainings on Tasso+™ administration prove adequate for this subsequent administration.

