2.3 Exploratory Objective

To evaluate the impact of prior training on subsequent Tasso+™ administrations.

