4.2 Steps to the Process

4.2.1 *Training*

Training will be provided on Days 1 and 29 and will include detailed IFU and online video training. The detailed IFU will be provided in a separate document, and an overview of IFU is provided in [Section 7.4](#). When administering the Tasso+™ remotely, participants will receive proctor-support from the Site on Day 29 (and as requested, on Day 57) during working hours, the intent being to guide the participant through the process and to help troubleshoot should any difficulties be encountered. Training on Day 57 should be performed only if it is specifically requested due to participant hesitation.

4.2.2 *Blood Collection*

Once trained, and by following the IFU provided (see [Section 7.4](#)), participants will self-administer the Tasso+™ device in the Clinic at the Investigator site (supervised) and subsequently remotely, ie, at home or a suitable remote location (proctor-supported on Day 29 and unsupported on Day 57). Self-collection may be additionally supported on Day 57 using a proctor session, as requested, to guide the participant through the process and help to troubleshoot any difficulties. The SST tube will be preferably collected from the left upper arm and the EDTA tube will be preferably collected from the right upper arm.

As per IFU, participants will have to gently invert the Tasso+™ capillary collection tubes after the full collection process is completed.

4.2.3 *Blood Volume and Clotting Analyses*

Blood volume and clotting analyses will be assessed before centrifugation. Thus, for Cohort B, on Day 1, these endpoints will be assessed by the Site, while for Cohort A, on Day 1 and for Cohorts A and B combined on Days 29 and 57, these endpoints will be assessed by the Central Laboratory (see [Section 6.3](#)).

4.2.4 *Centrifugation*

Tasso+™ blood samples of participants randomized to Cohort A, collected on Day 1, will be centrifuged upon receipt by the Central Laboratory, as per the real-world use of Tasso+™.

Tasso+™ blood samples of participants randomized to Cohort B, collected on Day 1, will be centrifuged and aliquoted by the Site before shipping, following the same procedure as for venipuncture blood samples.

Tasso+™ blood samples of participants from both Cohorts A and B, collected on Days 29 and 57, will be centrifuged upon receipt by the Central Laboratory, as per the real-world use of Tasso+™.

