Thus, for Cohort B, on Day 1, centrifugation and aliquoting will be performed by the Site, while for Cohort A, on Day 1 and for Cohorts A and B combined on Days 29 and 57, centrifugation and aliquoting will be performed by the Central Laboratory.

4.2.5 *Shipping*

On Day 1, Tasso+™ and venipuncture collection tubes will both be shipped by the Site following this visit.

On Days 29 and 57, blood will be shipped by the participant (remotely proctor-supported and unsupported, respectively).

4.2.6 *Hemolysis Analysis*

Hemolytic index will be assessed before testing by the Central Laboratory (see [Section 6.3](#)).

4.2.7 *Testing*

Upon receipt, both SST and EDTA samples will be tested by Central Laboratory (see [Section 6.3](#)).

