4.3 Management of Device Failures

Device failures, as a measure of reliability, will be assessed, as part of evaluating device performance.

Device failures due to deficiencies or malfunctions (see [Sections 8.1.6](#) and [8.1.7](#)) are defined as failure in activation of the lancet, or lack of any blood collection within 5 minutes.

Device failures due to user errors (see [Sections 8.1.8](#)) consist of incorrect attachment of the capillary collection tube to the device, damage to the device or the capillary collection tube upon handling, lack of maintained seal between the device and the skin surface of the participant, or incomplete trigger of the button (not fully pressing the button once the Tasso+™ device is sealed to the skin surface) (see [Section 6.3.3](#) for details).

On a case-by-case basis, in the event of collection failure, either related to user or device, as per the protocol-specific laboratory manual, an additional device/kit may be provided to the participant, so that proctor-supported or unsupported capillary blood collection can be performed for a second time, 1-inch away from the previous administration site.

A proctor session may be triggered by the participant (during working hours) in order to claim for help or report any concern related to the unsupported use of Tasso+™ device. Contact information will be provided to each participant in the event they have concerns or they need help while using Tasso+™ device.

In the event of collection failure, the participant should contact the Site for instructions on how the device should be returned to the clinic for evaluation.

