6.0 Study Design

Each participant will be followed with a study visit in the Clinic on Day 1, and subsequent decentralized, remote study visits on Days 29, 57, and 85. The total duration of study participation is planned to be 85 ± 3 days.

On Day 1, each participant will be randomized 2:1 to either Cohort A or Cohort B. Tasso+™ blood samples of participants randomized to Cohort A will be shipped to the Central Laboratory where they will be centrifuged and aliquoted. However, Tasso+™ blood samples of participants randomized to Cohort B will be centrifuged and aliquoted at the Site prior to shipping to the Central Laboratory, following the same approach used for venipuncture blood samples.

The decentralized visit on Day 29 (Visit 2) will be remotely supported by a prescheduled proctor during working hours to support the participant's self-administration of the Tasso+™ device. For the decentralized visit on Day 57 (Visit 3), the participant will have the option to request a prescheduled proctor session during working hours to support the participant's self-administration of the Tasso+™ device. The participant will use an electronic diary (eDiary) to report symptoms for 28 days following each Tasso+™ device administration (Symptom questionnaire) and to report on the usability of the Tasso+™ device (Tasso questionnaire) immediately following each Tasso+™ device administration (on Days 1, 29, and 57) and on Day 85. Contact information will be provided to each participant in the event they have concerns or they need help during working hours while using the Tasso+™ device.

Statistical Analysis Plan (SAP)

Protocol: Phase 1 Study Evaluating Technologies for Point-of-Care Blood Collections in Support of Decentralized Outpatient Assessments in Pandemic and Clinical Trial Settings

Version Date: 27-Jun-2025

Sponsor: Resilience Government Services, Inc.

Protocol No: 5309/0024

Venous blood collection (phlebotomy) will take place on Day 1; capillary blood collections using Tasso+™ device will take place on Days 1, 29, and 57; usability data will be collected after each use of Tasso+™ device and on Day 85; reliability of the device will be collected after each use of Tasso+™ device (Days 1, 29, and 57). Each Tasso+™ capillary blood collection will be followed by a 28-day follow-up period during which safety of the Tasso+™ device will be assessed using an eDiary (Symptom questionnaire).

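### The planned Day 57 proctor split cannot be read as an effect of prior training or of support, and Day 29 is never compared with Day 57 within participant

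*SAP*

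**What the plan says.** Protocol 2.3 gives the single exploratory objective: "To evaluate the impact of prior training on subsequent Tasso+™ administrations". The training schedule is common to all participants. Protocol 4.2.1 states "Training will be provided on Days 1 and 29 and will include detailed IFU and online video training", and Table 1 footnote c assigns the Day 1 session to the site and the Day 29 session to the proctor. For the last use, "Training on Day 57 should be performed only if it is specifically requested due to participant hesitation".

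Proctor support is routine on Day 29. For Day 57, SAP 6.0 says "the participant will have the option to request a prescheduled proctor session during working hours". Protocol 4.3 adds, for unsupported use, "A proctor session may be triggered by the participant (during working hours) in order to claim for help or report any concern". Protocol 6.2 describes Day 57 as intended to be unsupported, and it states a narrower interest: whether the earlier training is enough for that use.

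SAP 9.5.4.1 carries the analysis: "Descriptive statistics will be presented for participants who requested proctor support on the Day 57 Visit" and for those who completed Day 57 without a proctor. It covers sample integrity, reliability, safety and usability, all in the PPS. SAP 6.3.2 limits the PPS to participants with at least five successful administrations and no important protocol deviation.

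Elsewhere, sample integrity is summarized separately on Days 29 and 57 (SAP 9.5.2.1) and usability on Days 1, 29, 57 and 85 (SAP 9.5.3.3). Reliability is defined as one percentage over Day 1 to Day 57 (Protocol 3.1, SAP 9.5.2.3).

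**The concern.** To learn the impact of training, something in the data must vary training. By plan nothing does. The randomized cohorts differ in where and when Day 1 Tasso+ tubes are centrifuged, and the Day 57 groups differ in who asked for help. People who ask are likely to be those who expect difficulty or have met it, so a gap between the groups can arise with no effect of training or support. It could even point the wrong way and suggest that support harms performance.

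The PPS adds a second selection. Sample integrity and device failure are among the outcomes described, and entry to the PPS depends on having succeeded almost every time.

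Meanwhile the design contains a closer benchmark for the narrower question: each participant's own proctored Day 29 result. Days 29 and 57 are both remote, self-collected and shipped by the participant, and "for Cohorts A and B combined on Days 29 and 57, centrifugation and aliquoting will be performed by the Central Laboratory". The plan reports the two days side by side for integrity and usability, but never within participant, and it does not specify reliability by visit.

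**Working it through.** **1. The plan's own size figure.** Inputs: about 200 participants, 2:1 (Protocol 9.3, SAP 6.2). 200 × 2/3 = 133.3 and 200 × 1/3 = 66.7, which reproduces the stated 133 and 67. This split concerns centrifugation. The documents give no expected size for the Day 57 support groups and no formal basis for 200.

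**2. Where training could differ.**
- Day 1: everyone, by the site.
- Day 29: everyone, by the proctor.
- Randomization: centrifugation only.
- Day 57: on request, so any extra training goes with the choice to ask.

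By plan, then, training before Day 57 is the same in both groups.

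**3. What self-selection alone can produce.** Assume training and support have no effect. Let a share h of participants be hesitant with 70.0% success, and the rest confident with 93.4%. These rates are the low and high self-collection figures quoted in Protocol 1.2, used here only as an illustration. Hesitant participants request support with probability a, confident ones with probability c; h, a and c are assumptions.

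- Share requesting: r = h·a + (1−h)·c
- Success if supported: [h·a·0.70 + (1−h)·c·0.934] / r
- Success if unsupported: [h(1−a)·0.70 + (1−h)(1−c)·0.934] / (1−r)

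| h | a | c | r | Supported | Unsupported | Difference (points) |
|---|---|---|---|---|---|---|
| 0.2 | 0.2 | 0.2 | 0.200 | 88.7% | 88.7% | 0 |
| 0.2 | 0.4 | 0.1 | 0.160 | 81.7% | 90.1% | −8.4 |
| 0.3 | 0.6 | 0.05 | 0.215 | 73.8% | 89.8% | −16.0 |
| 0.3 | 0.8 | 0.05 | 0.275 | 73.0% | 91.5% | −18.5 |

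The difference is zero only when both types ask equally often.

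**4. What the PPS does.** Two tubes on three days make six planned administrations. Take success as a usable collection, independent across administrations with probability p (both are assumptions; SAP 6.3.2 does not define success).

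- P(at least 5 of 6) = p⁶ + 6p⁵(1−p)
- Success rate within the PPS = [p⁶ + (5/6)·6p⁵(1−p)] / P(at least 5 of 6)
- p = 0.70: 0.118 + 0.303 = 0.420 qualify; success among them is 88.0%.
- p = 0.934: 0.664 + 0.281 = 0.945 qualify; success among them is 95.0%.

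Where performance is poor, the PPS hides most of it: a true 70% appears as 88%.

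**5. Precision of a paired Day 29 to Day 57 change.** With n pairs, discordant share d and a net change near zero, SE = √(d/n). Assume 180 pairs and d from 10% to 25%; neither figure is in the documents.

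- √(0.10/180) = 2.4 points; 95% half-width 1.96 × 2.36 = 4.6
- √(0.25/180) = 3.7 points; 95% half-width 1.96 × 3.73 = 7.3

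**The case against.** The case for leaving the plan alone has real substance.

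- **The data are used.** A reader might infer that the Day 29 and Day 57 results go unused. They do not: integrity and usability are reported by day. Among people seen on both days, the paired estimate equals the difference of the two percentages. Pairing adds the count who changed in each direction, a fixed set of people and a valid interval. By-visit reliability is the element not specified.
- **The objective is partly served.** A reader might infer that it is not addressed at all. Whether earlier training suffices on Day 57 is largely a one-group question, and describing the unsupported completers speaks to it. SAP 9.3.1 also tabulates use with and without a proctor. What is lacking is a benchmark and a set not selected on success.
- **No effect is claimed.** SAP 9.5.4.1 is descriptive, exploratory and headed as proctor support, and no between-group difference is specified. That limits the harm. Still, it is the only output offered for an objective worded as an impact of training.
- **The paired change does not isolate training.** This stands in full. Day 29 is itself a training visit, so the change to Day 57 mixes withdrawal of routine support, the added Day 29 training, practice and time, possibly in opposing directions.
- **Identical training is only the plan.** SAP 9.5.4.2 records that collection instructions changed on 10 December 2024. Day 57 training is also on request, so the groups do not differ in support alone.

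**Conclusion.** The point holds as a mismatch between an objective and its analysis. No arm or planned comparison varies prior training. The Day 57 split is self-selected, mixed with same-day training, possibly a consequence of a problem, and restricted to a set that selects on the outcome. It should not be read as an effect of training or of support, and it answers the narrower question about Day 57 only in part.

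Its possible size is material: 8.4 to 18.5 points of apparent disadvantage with no true effect, under the unequal request rates assumed above, and an 18-point inflation of success in the PPS if true success were 70%. At 93.4% the PPS inflation is under 2 points. The documents give neither request rates nor within-person agreement, so these are illustrations, not predictions.

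Because the endpoint is exploratory and descriptive, this does not threaten the primary results. It is a worthwhile change because it needs only data already collected.

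**What to change.** Amend SAP 9.5.4.1 as follows.

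1. **Add a descriptive within-participant Day 29 to Day 57 summary**: paired 2×2 tables and the paired difference with a 95% confidence interval, for sample integrity by tube, device failure by visit and solicited local adverse events, with the corresponding paired change for usability items. Use all FAS participants with both visits, and show it again for those unsupported on Day 57.
2. **Present the Day 57 support split in the FAS**, with the PPS as a sensitivity analysis. Label it as use of support, not as an effect of training.
3. **State what the paired change means.** It shows whether performance holds when routine proctoring is withdrawn after training. It mixes withdrawal of support, the added Day 29 training, practice and time. Flag pairs that span the 10 December 2024 instruction change.

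The cost is a few extra descriptive tables and no new data. Two limits remain. The contrast does not isolate training. The unsupported subset is also self-chosen: if people whose Day 29 collection went well are more likely to decline support, their results may fall back on Day 57 by regression to the mean. The all-participant version should therefore come first.

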3.3 Exploratory Endpoint

The exploratory endpoint will evaluate the impact of prior training on subsequent Tasso+™ administrations using descriptive analyses of proctor-supported and proctor-unsupported Tasso+™ administrations on Day 57 using each of the following endpoints:

- Sample integrity
- Reliability
- Safety
- Usability

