4 STUDY PLAN

4.1 Overall Study Design and Plan

This is a Phase 1, multicenter, observational study that will evaluate the Tasso+™ device in approximately 200 male or female adult participants in an outpatient setting who are healthy or in well-compensated health at up to 5 US sites.

The Investigator will obtain electronically signed informed consent (eConsent form) from the participant before any study procedures are performed. For further details regarding the informed consent process, see [Section 11.3](#).

Each participant will be followed with a study visit in the Clinic on Day 1, and subsequent decentralized, remote study visits on Days 29, 57, and 85. The total duration of study participation is expected to be 85 ± 3 days.

On Day 1, each participant will be randomized 2:1 to either Cohort A or Cohort B. Tasso+™ blood samples of participants randomized to Cohort A will be shipped to the Central Laboratory where they will be centrifuged and aliquoted. However, Tasso+™ blood samples of participants randomized to Cohort B will be centrifuged and aliquoted at the Site prior to shipping to the Central Laboratory, following the same approach used for venipuncture blood samples.

The decentralized visit on Day 29 (Visit 2) will be remotely supported by a prescheduled proctor during working hours to support the participant's self-administration of the Tasso+™ device. For the decentralized visit on Day 57 (Visit 3), the participant will have the option to request a prescheduled proctor session during working hours to support the participant's self-administration of the Tasso+™ device.

The participant will use an electronic diary (eDiary) to report symptoms for 28 days following each Tasso+™ device administration (Symptom questionnaire) and to report on the usability of the Tasso+™ device (Tasso questionnaire) immediately following each Tasso+™ device administration (on Days 1, 29 and 57) and on Day 85. Contact information will be provided to each participant in the event they have concerns or they need help during working hours while using the Tasso+™ device.

Venous blood collection (phlebotomy) will take place on Day 1; capillary blood collections using Tasso+™ device will take place on Days 1, 29, and 57; usability data will be collected after each use of Tasso+™ device and on Day 85; reliability of the device will be collected after each use of Tasso+™ device (Days 1, 29, and 57).

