9.4.2 Secondary Endpoints

9.4.2.1 Safety

Counts and percentages will be presented for participants in the FAS who experience:

- Solicited local AEs (including pain, tenderness, redness, swelling, or bruising)

- Unsolicited AEs
- A related Grade 3 AE
- A related Grade 4 AE
- A related AE leading to discontinuation
- A related SAE

9.4.2.2 *Tolerability*

The counts and percentages of participants in the FAS who complete the Day 57 Visit will be summarized.

9.4.2.3 *Usability*

Descriptive statistics will be presented for participants in the FAS for each aspect of the usability questionnaire on Days 1, 29, 57, and 85.

9.4.2.4 *SARS-CoV-2 Infection Surveillance*

Counts and percentages will be presented for participants in the FAS for:

- Participants with a positive nasopharyngeal swab for SARS-CoV-2 PCR on Day 1
- Participants seroconverting to SARS-CoV-2 between Days 1 and 57

9.4.3 *Exploratory Endpoint*

Descriptive statistics will be presented for participants who requested proctor support on Day 57 Visit and for participants who completed the Day 57 Visit without using the proctor support, for the following primary and secondary endpoints:

- Sample integrity
- Reliability
- Safety
- Usability

9.4.4 *Analysis of Safety*

The SAS will be used for the analysis of safety data.

AEs will be coded with MedDRA. AEs are defined as events with an onset date on or after the date of first administration of the medical device and before the date of last administration of the medical device (Visit 3, Day 57 ± 3) +28 days, which corresponds to the Visit 4 (Day 85 ± 3). TEAEs will be presented by system organ class and preferred term in frequency tables. Participants with multiple AEs will be counted only once within each preferred term and system organ class.

Laboratory data (sodium, potassium, chloride, blood urea nitrogen, creatinine, glucose, phosphate, uric acid, and C-reactive protein) will be converted to Système International units for reporting and processing purposes. Absolute values will be presented descriptively. Laboratory data outside study-specific reference ranges will be listed.

9.4.5 *Demographic and Baseline Characteristics*

Demographic characteristics (including age, sex, ethnicity, and race) and baseline characteristics (including height, weight, BMI, supine systolic and diastolic blood pressure, pulse, body temperature, and respiratory rate) will be presented descriptively.

Prior and concomitant medications will be listed.

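### The Day 57 unsupported group is fixed only after the attempt, so failed unsupported uses can leave it and tilt the exploratory training comparison in its favour

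*SAP*

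**What the plan says.** The exploratory objective (protocol 2.3) concerns the effect of earlier training on later use of the device. Protocol 3.3 states the endpoint per administration: "descriptive analyses of proctor-supported and proctor-unsupported Tasso+™ administrations on Day 57".

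The analysis groups participants instead. SAP 9.5.4.1 compares "participants who requested proctor support on the Day 57 Visit and for participants who completed the Day 57 Visit without using the proctor support", within the PPS. Protocol 9.4.3 has the same second group, "participants who completed the Day 57 Visit without using the proctor support", without the PPS restriction.

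The documents describe two ways of obtaining a proctor on Day 57:

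- **In advance.** Protocol 4.1: "the participant will have the option to request a prescheduled proctor session during working hours". Schedule of Assessments, footnote c: "Proctor sessions will be prescheduled by the Site to take place during working hours".
- **When trouble arises.** Protocol 4.3, on unsupported use: "A proctor session may be triggered by the participant (during working hours) in order to claim for help or report any concern". The same section allows, case by case, a second attempt after a failed collection, with or without a proctor.

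Neither document says by when a request must be made to count, or where an unsupported use followed by proctor help belongs. Completion is not defined for this analysis. The only Day 57 definition is in SAP 9.5.3.2, for tolerability, where one of the two tubes is enough.

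**The concern.** A participant counts as unsupported only if they completed the visit and did not use a proctor. Both conditions depend on how the attempt went. Someone who starts alone, runs into trouble and calls for help has used support, so the wording removes them. Someone who starts alone, fails and does not complete is removed too. These are the cases that would show earlier training to be insufficient.

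Grouping by participant adds to this. One person can have both an unsupported and a supported use on Day 57, and no rule separates them.

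At stake is the only analysis of the training objective. Both documents also justify the sample of about 200 by the range of experience with unsupported use (protocol 9.3, SAP 6.1).

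**Working it through.** **Planned figures.** The plan states no group size, failure rate or margin for this comparison, so there is nothing to reproduce. The cohort split does reproduce (200 × 2/3 = 133.3; 200 × 1/3 = 66.7), but it does not bear on the point.

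**Step 1. Where each course of Day 57 lands.**

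| Course on Day 57 | Requested support | Completed without using it |
|---|---|---|
| Prescheduled session, used | yes | no |
| No session, both tubes obtained | no | yes |
| No session, one use fails, no call | no | yes, on the one-tube reading |
| No session, trouble, session triggered | not stated | no |
| No session, both uses fail, no call | no | no |
| Requested, not used, visit completed | yes | yes |

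The fourth and fifth rows leave the unsupported group because of what happened during the attempt. The third row stays. The last row fits both groups.

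**Step 2. Triggered sessions (illustration; all inputs assumed).** 150 participants start unsupported (300 uses) and 50 have a prescheduled session (100 uses). The true failure rate is 10% in both, giving 30 and 10 failed uses. Each failure is in a different participant, there are no replacement kits, and a caller's two uses both began before the call. Let k of the 30 failing unsupported participants call. Grouping is by participant, so both of a caller's uses leave.

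- Unsupported: (30 − k)/(300 − 2k)
- Supported, callers in neither group: 10/100
- Supported, callers counted as requesters: (10 + k)/(100 + 2k)

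| k | Unsupported | Supported, callers in neither | Supported, callers as requesters |
|---|---|---|---|
| 0 | 30/300 = 10% | 10% | 10/100 = 10% |
| 15 | 15/270 = 5.6% | 10% | 25/130 = 19.2% |
| 30 | 0/240 = 0% | 10% | 40/160 = 25% |

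**Step 3. The completion rule alone (FAS, one-tube reading, nobody calls).** Take two independent uses per participant, each failing with probability q. Unsupported participants drop out only if both uses fail. The rate left among their uses is 2q(1 − q) / [2(1 − q²)] = q/(1 + q). Supported participants are not filtered on completion and show q.

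Two failure figures from studies cited in protocol 1.2 serve as assumed per-use rates: 6.6% (100 − 93.4, unsupervised setting) and 30% (100 − 70.0).

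- q = 6.6%: 0.066/1.066 = 6.2% against 6.6%
- q = 30%: 0.30/1.30 = 23.1% against 30.0%

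**Step 4. With the SAP's PPS restriction.** The PPS needs at least five successful administrations out of six scheduled, so at most one failure. Assume independent uses, no replacement kits and no important deviations. If nobody calls, both groups show q/(1 + 5q): 0.066/1.33 = 5.0% in each, or 0.30/2.5 = 12.0% in each. The PPS lowers both rates equally and creates no gap by itself.

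Now let half of the unsupported starters with a Day 57 failure call, at q = 6.6%.

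- Unsupported: 0.033/(0.934 + 0.264 + 0.066) = 0.033/1.264 = 2.6%
- Supported, callers in neither group: 5.0%
- Supported, callers as requesters, half prescheduled: (0.0330 + 0.0165)/(0.665 + 0.033) = 7.1%
- Supported, callers as requesters, one fifth prescheduled: (0.0132 + 0.0264)/(0.266 + 0.0528) = 12.4%

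**Step 5. After the change.** If all uses are classed by status at their start and all started uses are kept, Step 2 gives 30/300 and 10/100 for every k. Step 3 gives q in both groups.

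**The case against.** The strongest reply is that requests are planned in advance (protocol 4.1; footnote c), so the supported group is fixed before the attempt. This stands in part. A reader might infer that the plan moves failed unsupported uses into the supported group, but no text says so; it is one of two open readings. It does not rescue the unsupported group, whose definition excludes anyone who used support.

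The size is also open. With no calls, the gap is nil in the PPS and 0.4 points in the FAS at a 6.6% rate. That stands: the rescue share is not documented, and replacement kits, which Step 2 ignores, could change the picture.

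Three stronger readings are tempting and not supported:

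- **Training will look adequate whatever the truth.** At a 30% true rate with no calls, the unsupported group in the FAS still shows 23.1%.
- **The question cannot be answered at all.** A failure with no call in a completed visit stays in the group. Failed uses also remain in the FAS results for Day 57 sample integrity, device failures and Day 57 completion (SAP 9.5.2.1, 9.5.2.3, 9.5.3.2).
- **Five more failing participants drop out as non-completers, giving 10/260 = 3.8%.** In Step 2 each has one failed and one successful tube, so the only Day 57 completion definition counts them as complete.

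Support on request is the stated design, so self-selection is a limitation to report, not an error. The mismatch of unit is modest, since integrity and reliability are still proportions of samples and uses.

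**Conclusion.** The point holds as a possible bias of unknown size. The unsupported group is conditioned on the outcome of the attempt, and the plan leaves the place of rescued users unstated. Failures can leave that group, and the direction favours unsupported use.

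At an equal 10% true rate with half of the failing unsupported participants calling, the report shows 5.6% against 10% or 19.2%, depending on where callers are placed. The completion rule alone gives 6.2% against 6.6%, or 23.1% against 30.0%. These figures rest on assumed failure rates, independent uses and an assumed rescue share. The problem does not depend on the PPS: Steps 2 and 3 do not use it.

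The endpoint is exploratory and descriptive, with no hypothesis test (SAP 9.5.1). No primary or secondary conclusion is affected. The change is still worth making, because this is the only analysis of the training objective.

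**What to change.** In SAP 9.5.4.1 and protocol 9.4.3:

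1. Classify each Day 57 device use by its support status when that use began: supported if a prescheduled proctor session was in place, otherwise unsupported.
2. Keep a use as unsupported if a session was triggered after trouble arose. Count any re-attempt under its own status at its start.
3. Include every started Day 57 use, whether or not the visit was completed.
4. Report the number of unsupported uses followed by a triggered session.
5. State that support was self-selected and that the contrast is not causal. Optionally show each group's Day 29 integrity and failure results beside it.

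The cost is wording and one derived flag. The sources are the Site's schedule of proctor sessions (footnote c), the with or without proctor data already tabulated by visit (SAP 9.3.1) and the recorded collection times (protocol 7.4). The documents do not say that the time of a request or session is captured. This should be confirmed, and any use whose status cannot be established reported as such. The unsupported results may look less favourable.
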